2. STUDY DESIGN

2.1. Rationale for study design and objectives

For this study, blood samples will be collected on a calendar basis: Day -7, day 7, day 14, day 21, day 28, day 56, day 100, day 180 and day 360 post-HCT, as well as at appearance of clinical symptoms suggestive of acute GVHD and that trigger treatment with systemic steroids. A saliva sample will also be collected at the day-7 and day +56 time-points from subjects with a HCT white blood cell count of <400/µL to provide an additional specimen for DNA extraction. Samples will be processed at local sites and will then be shipped to the Indiana University Simon Cancer Center (the Data and Specimen Coordinating Center) from the other five participating Blood and Marrow Transplant Programs (Dana-Farber Cancer Institute and Boston Children's Hospital, Johns Hopkins Sidney Kimmel Comprehensive Cancer Center, Fred Hutchinson Cancer Research Center, Texas Children's Hospital, and Children's National Medical Center). The appropriate samples will be transported to [name] laboratory for analysis of a seven-protein biomarker panel. The results from previous discovery and validation studies suggested that the panel of six biomarkers can confirm the diagnosis of acute GVHD in patients at onset of clinical symptoms of acute GVHD and provide prognostic information independent of acute GVHD severity. Furthermore, suppression of tumorigenicity 2 measured at initiation of therapy can predict day 28-non-response and the day 180-post treatment non-relapse mortality in patients with GVHD treated with at least systemic corticosteroids. ST2 outperforms all previously identified biomarkers for prognostic information. The plasma protein biomarker panel will include at minimum: interleukin-2-receptor-alpha, tumor-necrosis-factor-receptor-1, interleukin-8, hepatocyte growth factor, elafin, regenerating islet-derived 3-alpha and suppression of tumorigenicity 2.

Primary Objective: The primary objective is to confirm that ST2 alone or the sevenbiomarker panel measured at initiation of GVHD therapy predict a) D180 post-therapy non-relapse mortality; b) D28 post-therapy non-response, and c) GVHD grade 1-4 onset.

Secondary Objective:

- 1. To demonstrate that ST2 alone or the seven-biomarker panel measured at day 14 or day 21 post-HCT (or a combination of these time points) predict D180 post-HCT non-relapse mortality.
- 2. To demonstrate that ST2 alone or the seven-biomarker panel measured at initiation of GVHD symptoms/therapy diagnose acute GVHD as compared to other complications presenting with similar symptoms (drug rash, CMV, Clostridium enteritis).
- 3. To demonstrate that ST2 alone or the seven-biomarker panel measured at initiation of GVHD symptoms/therapy diagnose the severity of acute GVHD at onset and maximum.
- 4. To develop a repository of biospecimens linked to clinical data for future unspecified research.

2.2. Eligibility

- All patients receiving an allogeneic hematopoietic stem cell transplant, cord blood transplant, bone marrow transplant, T cell depleted marrow, donor lymphocyte infusion (DLI), or donor cellular infusion (DCI) can be included.
- Patients (or parent/guardian) must have signed the informed consent document

2.3. Accrual objective and period

- Accrual objective: Sample size 430
- Accrual period: The estimated accrual period is 24 months

2.4. Study duration: Patients will be followed for 12 months following initiation of GVHD therapy or 12 months post-HCT for non-GVHD patients.

- This study will not require any extra clinic visits beyond those required for routine clinical patient care.
- For subjects who consent to the future unspecified use of their biospecimens for research purposes, clinical data collected at any time post-transplant as part of routine clinical care may also be accessed.

3. STUDY ENDPOINTS

3.1. Primary endpoint: The primary objective is to confirm that ST2 alone or the seven-biomarker panel measured at initiation of GVHD therapy predict a) D180 post-therapy non-relapse mortality; b) D28 post-therapy non-response, and c) GVHD grade 1-4 onset.

3.2. Secondary endpoints:

- 1. To demonstrate that ST2 alone or the seven-biomarker panel measured at day 14 or day 21 post-HCT (or a combination of these time points) predict D180 post-HCT non-relapse mortality.
- 2. To demonstrate that ST2 alone or the seven-biomarker panel measured at initiation of GVHD symptoms/therapy diagnose acute GVHD as compared to other complications presenting with similar symptoms (drug rash, CMV, Clostridium enteritis).
- 3. To demonstrate that ST2 alone or the seven-biomarker panel measured at initiation of GVHD symptoms/therapy diagnose the severity of acute GVHD at onset and maximum.

3.3. Clinical and histological correlatives:

• Pre-transplant characteristics

Age at transplant, gender, race and ethnicity, Disease diagnosis, disease risk (CIBMTR classification), intensity of conditioning, conditioning regimen, donor source,

HLA-match, stem cell source, other significant pre-HCT diagnoses and clinical characteristics

- GVHD prophylaxis
- Infectious prophylaxis, if any
- Onset Acute GVHD: day of onset, skin stage, liver stage, gastrointestinal stage and overall grade.
- Maximum Acute GVHD: day max, skin stage, liver stage, gastrointestinal stage and max overall grade.
- Biopsies:
 - - yes No,
 - o location skin, upper GI, lower GI, liver
 - GVHD yes or no, other diagnostic, specify
 - This will help identify the incidence of other complications presenting with GVHD symptom that is not GVHD (e.g. infectious diarrhea, drug rash...)
- Systemic therapy
 - Start day
 - Steroids 2 mg/kg/day Yes No
 - Other first line
- Proportion of complete response (CR), Partial response (PR), mixed response, No response, and progression at day 28 post-therapy (among surviving patients)
- Incidence of additional therapy of GVHD given at day 28, and day 56 posttherapy (including for GVHD flare).
- Non-relapse mortality (NRM) at day 180 post-therapy for GVHD patients and NRM at day 180 post-HCT for patients without GVHD.
- Overall survival, GVHD-free survival at day 180 and 360 post-therapy for GVHD patients and NRM at day 180 and 360 post-HCT for patients without GVHD.
- Relapse at day 360 post-HCT.
- Incidence of systemic infections related to GVHD treatment.
- Incidence of chronic GVHD at day 180 and day 360.

• For subjects consenting to future unspecified research, data collected at any time-point post-transplant as part of routine clinical care may be accessed for future studies.

Staging and grading of acute GVHD

In this study we will classify patients by a modified Keystone grading schema (see below).

Table 1: Acute GVHD Staging								
Stage	Skin	Liver (bilirubin)	Lower GI (stool output/day)	Upper GI				
0	No rash	≤ 2 mg/dl	Adult: < 500 ml/day Child: < 10 ml/kg/day	No protracted nausea and vomiting				
1	Maculopapular rash < 25% BSA	2.1-3 mg/dl	Adult: 500–1000 ml/day Child: 10 -19.9 ml/kg/day	Persistent severe nausea, vomiting with a positive upper GI biopsy				
2	Maculopapular rash 25 – 50% BSA	3.1-6 mg/dl	Adult: 1001-1500 ml/day Child: 20 – 30 ml/kg/day					
3	Generalized erythroderma (>50% BSA)	6.1-15 mg/dl	Adult: >1500 ml/day Child: > 30 ml/kg/day					
4	Generalized erythroderma (>50% BSA) plus bullous formation and desquamation > 5% BSA	>15 mg/dl	Severe abdominal pain with or without ileus, or grossly bloody stool or melena (regardless of stool volume)					

For GI staging:

- The "adult" stool output values should be used for patients > 50 kg in weight.
- Use 3 day averages for GI staging based on stool output. If stool and urine are mixed, stool output is estimated to be 50% of total stool/urine mix.

Table 2: Overall Acute GVHD Clinical Grade:						
Grade 0:	No stage 1-4 of any organ					
Grade I:	Stage 1-2 skin and no liver or gut involvement					
Grade II:	Stage 3 skin, or Stage 1 liver, or Stage 1 Gl					
Grade III:	Stage 0-3 skin, with Stage 2-3 liver, or Stage					
2-3 GI Gra	de IV: Stage 4 skin, liver or GI					

Response Definitions:

Complete Response (CR) is defined as a GVHD grade of 0 in all evaluable organs. For a response to be scored as CR at day 28, the patient must still be in CR on that day and have had no intervening additional therapy for an earlier progression, PR or NR.

Partial Response (PR) is defined as improvement in one or more organs involved with GVHD symptoms without progression in others. For a response to be scored as PR at day 28, the patient must still be in CR on that day and have had no intervening additional therapy for an earlier progression, PR or NR.

Mixed Response (MR) is defined as improvement in one or more organs with deterioration in another organ manifesting with GVHD symptoms or development of GVHD symptoms in a new organ.

Progression is defined as deterioration in at least one organ without any improvement in others.

No response (NR) is defined as absence of any improvement or progression as defined. Patients receiving secondary therapy (including need to re-escalate steroid dose to \geq 2.5 mg/kg/day of prednisone or equivalent 2 mg/kg/day of methylprednisolone will be classified as non-responders.

Proportion of complete response (CR), Partial response (PR), mixed response (MR), progression, and no response (NR) at day 28 post-therapy (among surviving patients). Scoring of CR, PR, MR, progression, and NR are in comparison to the patient's acute GVHD status on day 0 of systemic therapy for GVHD.

Incidence of additional systemic GVHD therapy given at day 28, and day 56 posttherapy (including for GVHD flare).

Flares are defined as any progression of acute GVHD after an initial response (e.g. earlier CR or PR) that requires re-escalation of steroids or initiation of additional systemic therapy for GVHD.

Steroid dose at day 28 and day 56 post-GVHD therapy

Dose of methylprednisolone will be converted to prednisone by multiplying the methylprednisolone dose by 1.25. Prednisone dose for each patient will be converted to mg/kg. The cumulative prednisone dose for each patient at day 28 will be calculated by adding the doses (end of each week's dose) for each of the four weeks of treatment, divided by the number of days of survival during this interval. The prednisone dose for each patient at day 28 and day 56 will be recorded.

Chronic GVHD is defined per the BMT CTN manual of procedures chapter 2. Symptoms of chronic GVHD if present will be reported using the GVHD symptom record. The incidence of chronic GVHD at 6 and 12 months will be computed.

Non-relapse mortality (NRM) at day 180 post-therapy for GVHD patients and NRM at day 180 post-HCT for patients without GVHD will be computed. The events for NRM are death due to any cause other than relapse of underlying malignancy.

Overall survival, GVHD-free survival at day 180 and 360 post-therapy for GVHD patients and at day 180 and 360 post-HCT for patients without GVHD will be computed.

Relapse at day 360 post-HCT will be computed.

Incidence of systemic infections related to GVHD treatment through day 180 posttherapy for GVHD patients and day 180 post-HCT for patients without GVHD will be computed. All microbiologically documented infections (bacterial and fungal) or significant infections requiring antibiotic/antifungal therapy occurring within 6 months of initiation of therapy for GVHD patients or 6 months post-HCT for no-GVHD patients will be reported by site of disease, date of onset, and severity. For definitions, see the BMT CTN manual of procedures.

Incidence of severe viral infections related to GVHD treatment through day 180 post-therapy and in no-GVHD patients will be recorded (EBV-PTLD, CMV viremia, HHV6 encephalitis...).

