Science Translational Medicine¹³. This data provides a proof-of-principle demonstration that biomarkers of disease-related, tissue-specific changes can be detected in the plasma of patients. We used this approach as the basis for extension of the validation of plasma GI biomarkers. We identified Regenerating Islet-Derived 3-alpha (REG3 α) as a biomarker of lower gastrointestinal GVHD and validated it in 2 independent sets totaling 1014 patients from three different centers. We showed that plasma REG3a concentration at the onset of GVHD diarrhea is the best biomarker (i) to differentiate GVHD diarrhea from non-GVHD diarrhea; and (ii) to provide important prognostic information, including eventual response to GVHD treatment and survival. We also showed that the addition of this marker to clinical stage and histologic grade leads to a more refined grading system and risk stratification of patients at the time of GVHD diagnosis. This was recently published in *Blood*¹⁴.

Further, we first validated elafin as biomarker of resistance to GVHD treatment (unpublished data). As shown in Figure 3, we performed additional measurements at four weeks post-treatment and correlated the

concentrations of elafin with the response to GVHD treatment. Patients with complete response (CR) at four weeks exhibited no rash symptoms and had concentrations of elafin in the range of patients without GVHD (white bar), whereas patients with persistent or progressive rash (No-CR) (30% of the population) had unchanged elafin concentrations. Likewise, measurements TNFR1 of concentrations

declined as compared to the onset in patients who had a complete resolution of GVHD symptoms ²⁸.

Fig 3. Elafin concentrations at onset and 4week post-treatment in CR and No CR patients (paired t-test)

These studies have been among the first to apply proteomic technology to identify biomarkers for GVHD, yet blood tests were still not able to predict a patient's response to therapy, particularly at GVHD onset, when risk-stratification is most beneficial. We hypothesized that biomarkers discovered with an intact proteomic analysis system (IPAS) approach that we have described above will discriminate between therapy responsive (resolution or improvement of GVHD by day (D) 28 post-therapy initiation) and unresponsive (absence of complete or partial response) patients and predict survival in patients receiving GVHD therapy.

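### The day-28 scoring rule for partial response requires complete response, so improved patients with residual GVHD cannot be scored as partial responders

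*Protocol*

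**What the plan says.** The response categories are in Protocol section 3.3, under Response Definitions.

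- **CR** is grade 0 in all evaluable organs. Its day-28 rule reads "For a response to be scored as CR at day 28, the patient must still be in CR on that day", with the further condition of no intervening additional therapy.
- **PR**: "Partial Response (PR) is defined as improvement in one or more organs involved with GVHD symptoms without progression in others". Its day-28 rule reads "For a response to be scored as PR at day 28, the patient must still be in CR on that day", with the same condition on therapy.
- **Mixed response (MR)** needs improvement in one organ together with deterioration in another or a newly involved organ.
- **Progression** needs deterioration in at least one organ and improvement in none.
- **No response (NR)**: "No response (NR) is defined as absence of any improvement or progression as defined".
- **Secondary therapy** overrides the categories. The sentence begins "Patients receiving secondary therapy (including need to re-escalate steroid dose to" and ends by saying that such patients "will be classified as non-responders".

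Two other places show how PR was meant to count. Section 1.3 separates responsive patients from the rest in these terms: "resolution or improvement of GVHD by day (D) 28 post-therapy initiation) and unresponsive (absence of complete or partial response) patients". In section 3.3 the flare definition treats PR as a response: "Flares are defined as any progression of acute GVHD after an initial response (e.g. earlier CR or PR".

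Day-28 non-response is primary endpoint b (section 3.1). Appendix C (Biomarker Panel) calls a marker high when it is more than 50% above the responder group's median. It calls a panel high when at least five markers are high, and uses high or low panel with onset grade to form four risk categories for day-180 non-relapse mortality (NRM). Neither section 3 nor Appendix C lists the categories that make up non-response or the responder group.

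**The concern.** A patient whose GVHD has improved but not cleared is the ordinary partial responder. The PR definition covers that patient, and the operative day-28 rule shuts the same patient out. An analyst who programmes the rule as written has to leave these patients unclassified or place them with the non-responders.

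Either choice changes who is counted in primary endpoint b. It also takes these patients out of the responder group, so the Appendix C median would come from complete responders alone. That cutoff then feeds the high and low panel groups used for day-180 NRM.

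**Working it through.** There is no stated figure to reproduce. The check sets the definitions against every possible day-28 outcome.

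**Inputs.** The CR, PR, MR, progression, NR and secondary-therapy rules of section 3.3. Outcomes are compared with GVHD status on day 0 of systemic therapy, as that section requires. A newly involved organ is counted as deterioration.

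**Step 1: possible patterns.** Classify each patient by improvement in any organ, deterioration in any organ, and residual GVHD at day 28, each yes or no. A patient with GVHD at day 0 and none at day 28 must have improved and cannot have deteriorated, which gives 1 pattern. With residual GVHD, improvement and deterioration can combine freely, which gives 2 × 2 = 4. The total is 1 + 4 = 5.

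**Step 2: assign categories, no secondary therapy.**

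| Improved | Deteriorated | Residual GVHD | By the definitions | With the literal day-28 PR rule |
|---|---|---|---|---|
| Yes | No | No | CR; also meets the PR definition | CR; also meets the PR rule |
| Yes | No | Yes | PR | Not PR: no category, or NR if NR is a catch-all |
| Yes | Yes | Yes | MR | MR |
| No | Yes | Yes | Progression | Progression |
| No | No | Yes | NR | NR |

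Only the second row changes. That patient is not CR, because disease remains. The patient is not PR at day 28, because CR is required. Nor is the patient MR or progression, because nothing deteriorated. NR depends on how its closing qualifier is read. If it requires that no improvement occurred, the patient is not NR. If it sweeps in anyone who met none of the defined responses, the patient is NR and so a non-responder.

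**Step 3: secondary therapy.** All 5 patterns are then non-responders by rule. Of the 5 × 2 = 10 combinations of pattern and therapy, 1 is affected.

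**Step 4: does section 1.3 settle it?** Its first half calls improvement responsive, which puts the second-row patient with the responders. Its second half defines unresponsive by the absence of CR or PR. If PR is scored literally, the same patient also meets that description. The intention is clear, but the wording depends on the faulty sentence and does not override it.

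**Step 5: the CR and PR overlap.** The first row meets the PR definition before any day-28 rule is applied, since there is improvement and no progression. Correcting the day-28 sentence alone would therefore leave CR patients inside PR. A precedence rule is needed as well.

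**The case against.** The strongest reply is that this is a copying slip with an obvious meaning. The PR sentence repeats the CR sentence, section 1.3 and the flare definition both treat PR as response, and section 3.3 lists PR as a proportion to be reported separately from CR, which makes little sense if PR requires CR. This stands as evidence of intent. It does not give the analyst an operative rule, because no passage corrects the sentence.

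A second reply is that endpoint b is binary, while the five categories sit under clinical and histological correlatives. That is true of the layout. But section 3 offers no other definition of day-28 response, so the binary endpoint has to be built from these categories.

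A third reply is that the catch-all reading of NR leaves nobody unclassified. That is a fair reading, and it means a reader should not infer that these patients certainly fall outside every category. On that reading they become non-responders, against the sense of section 1.3, so the faulty sentence still decides their endpoint status.

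A reader might also infer that the sentence creates the overlap between CR and PR. It does not, because the PR definition alone already covers patients in CR.

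**Conclusion.** The day-28 PR rule is wrong as written. It contradicts the PR definition beside it and leaves one of five response patterns, in patients without secondary therapy, either unassigned or counted as non-response. It bears on primary endpoint b and on the responder group behind the Appendix C cutoff, and through that cutoff on the panel groups for day-180 NRM.

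The size in patients cannot be derived, because the documents give no PR share. It might be tempting to infer a shift in the planned non-response rate of 0.41 or a loss of power. Neither follows, since no passage links that rate to this sentence. The direction of any change in the responder median is also unknown.

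Nor do the documents support an inference that reported results are affected. Nothing shows the rule was applied literally. The 2020 SAP analyses NRM and acute GVHD, with marker groups split at the whole-cohort day-21 median, and includes neither day-28 response nor a responder-group cutoff. The effect is confined to the protocol's endpoint b and Appendix C.

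The conclusion rests on the wording alone, with a new organ counted as deterioration.

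**What to change.** 1. In section 3.3, reconcile the two PR sentences with section 1.3 and the flare definition, so that the day-28 PR rule refers to the PR definition and not to CR.
2. In the same place, state that a patient who meets CR is scored CR and not PR.
3. In section 3 and in Appendix C, state which categories form day-28 non-response and which form the responder group whose median sets the high-marker cutoff.

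The cost is one corrected sentence, one clause on precedence, and one added sentence in each of section 3 and Appendix C. Section 4.2 already requires organ staging at onset and 28 days after systemic therapy, so the categories can be derived from data already planned.

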4.2. Study monitoring

The follow-up schedule is outlined in Table 3 (see below).

Table 3: Required assessments													
	All allogeneic HCT, day pre/post-HCT							post-	НСТ	GVHD +	Day post- GVHD systemic therapy		Chimerism
	-7	7	14	21	28	56	100	180	360	Onset (0)	28	56	If Standard of Care in Center
Biopsy of involved tissue (as part of routine clinical care, not research)										х			
Acute GVHD evaluation ^		Х	Х	Х	Х	Х	Х	Х		Х	Х	Х	
Chronic GVHD evaluation ^							Х	Х	Х				
Steroid dose		Х	Х	Х	Х	Х	Х	Х		Х	Х	Х	
Other GVHD medications, doses, and drug levels collected as part of clinical care		x	x	х	x	х	х	x	x	х	х	x	
Blood Samples*	Х	Х	Х	Х	Х	Х	Х	Х	Х	Х	Х		
Saliva DNA (if WBC < 400/µL)	х					Х							
Chimerism (% donor) ‡ **													Х

*Up to day 28, sample collection may be ± 4 days from the target day to allow for scheduling flexibility, holidays, etc...

*Day 100,180, and 360, sample collection will be collected at the clinic visit closest to the scheduled time point to allow for scheduling flexibility, holidays, etc...

*GVHD onset sample will be collected within a 48 hour window of systemic treatment initiation if subject is inpatient

‡ Donor chimerism results recorded at the time nearest to each sample collection will be noted.

^ Refer to Appendix D for GVHD assessment forms

** Will only collect data if already being done as standard of care at center

The timing of follow-up visits is based on the date of BMT and then on the

date of onset of GVHD for post-GVHD assessments.

Assessments

- Baseline weight
- For all, complete acute GVHD staging and grading information including assessment of rash, diarrhea, nausea/vomiting, liver function and weight at day
 - 7, 14, 21, 28, 56, 100, and 180 post-HCT
- If GVHD or GVHD-like symptoms,
 - recommended biopsy of involved tissue (this is standard of care, not research)
 - Complete acute GVHD staging and grading information including assessment of rash, diarrhea, nausea/vomiting, liver function and weight at onset of symptoms and 28 and 56 days post-systemic GVHD therapy
 - Steroids dose weekly until day 56
 - $_{\odot}$ Samples for laboratory studies at day -7, 7, 14, 21, 28, 56,100 and 180

post-HCT and at onset of GVHD symptoms, and 28 days post-systemic

- GVHD therapy
- Chronic GVHD evaluation at day 100, 180 and 360
- Infections requiring therapy up to 360 days post-HCT

Sample Collection

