Maximum volume of blood with each complication	15 mL	10 mL	7.5 mL	5 mL
Maximum volume for scheduled blood draws (9 collections)	135 mL	90 mL	67.5 mL	45 mL
Maximum blood volume if develops acute GVHD (2 collections)	30 mL	20 mL	15 mL	10 mL
Maximum blood volume for other complications (4 collections)	60 mL	40mL	30 mL	20 mL
Maximum volume collected in year one (scheduled plus collections with complications)	225 mL	150 mL	112.5 mL	75mL

Table 4: Summary of maximum blood volume to be collected for this study

*Cumulative blood volume will be monitored for each subject and individual blood draws will be decreased as needed to maintain annual cumulative blood collection of <10% of total blood volume.

Also note, for pediatric patients, we expect patient weights to increase over time due to normal growth and as such, updated patient weights will be used to re-calculate permitted blood volume collections every six months.

GVHD scoring

Acute GVHD

A sample Acute GVHD data record for use in this trial is attached below.

Today's Clinical Acute GVHD Assessment						
Today's date Patient ID		Karnofsky/Lansky				
Codes		Differential diagnosis				
0 1 2 3 4		GVHD Drug Cond Infect TPN VOD Other				
		Rxn Reg				
Skin 🗆 🗆 🗆 🕬	oody rash:					
Liver 🗆 🗆 🗆 🗆 Curr	ent bili: [Lower				
GI 🗆 🗆 🗆 🗆 Vol:		□ □ □ □ Upper GI				
		Systemic				
agents: 🗌 CSA 🗌	Tacrolimus	🗌 Infliximab 🛛 🗍 Daclizimab				
Pentost	atin 🛛 Sirolimu	s				
Prednis	one 🗌 Methylp	rednisolone 🗌 Ontak 🗌 Other				
Current steroid dose: Prednisone	mg/	kg/day; Methylprednisolone mg/kg/day				
Has the steroid dose been increased to $\ge 2.5 \text{ mg/kg/day}$ of prednisone (or 2 mg/kg/day methylpred)? \square YES \square NO If yes, data dose increased						
Topical agents: Skin topical steroids: YES NO; Non-absorbed oral steroids (e.g. Budesonide, Entocort) Image: Chronic GVHD: Does the patient have evidence of chronic GVHD? YES NO						
Codes Skin	Liver (bilirubin)	Lower GI (stool output/day) Upper GI				
0 No rash	≤ 2 mg/dl	Adult: < 500 ml/dayNo protracted nausea andChild: < 10 ml/kg/day				
1 Maculopapular rash < 25% BSA	2.1-3 mg/dl	Adult: 500–1000 ml/dayPersistent severe nausea, vomiting with a positive upper GI biopsy				
2 Maculopapular rash 25 – 50% BSA	3.1-6 mg/dl	Adult: 1001-1500 ml/day Child: 20 – 30 ml/kg/day				
3 Generalized erythroderma (>50% BSA)	6.1-15 mg/dl	Adult: >1500 ml/day Child: > 30 ml/kg/day				

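### The day-28 cumulative prednisone dose is defined as a sum divided by days alive, so it is not a cumulative dose; if the summed values are daily doses, it is also one seventh of their mean

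*Protocol*

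**What the plan says.** The rule stands in protocol section 3.3, under the sub-heading on steroid dose at days 28 and 56 after GVHD therapy. Methylprednisolone is first multiplied by 1.25 to give prednisone. Then "Prednisone dose for each patient will be converted to mg/kg", with no statement of whether this is per day or per week. The rule itself has two parts:

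- the quantity: "The cumulative prednisone dose for each patient at day 28 will be calculated by"
- the calculation: "adding the doses (end of each week's dose) for each of the four weeks of treatment, divided by the number of days of survival", where the days counted are those within the interval

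The prednisone dose at day 28 and at day 56 is recorded separately.

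Two other places bear on what is being added. Section 4.2 asks for "Steroids dose weekly until day 56", and the summary of required assessments repeats the weekly frequency. The sample acute GVHD data record, in section 4.2 and again in Appendix D, has a field "Current steroid dose: Prednisone" whose units read "kg/day; Methylprednisolone mg/kg/day". It has no field for a weekly total.

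The SAP does not mention steroid dose, so it neither repeats nor corrects the rule.

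**The concern.** There are two separate problems. The name promises a total in mg/kg, but the last step divides by days alive and turns any total into a rate. And if each term is one daily dose taken at the end of a week, the numerator covers four days' dosing while the denominator counts up to 28 days. No step multiplies each weekly record by seven.

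At stake is a description of steroid exposure. A reader given a value of 0.286 as a cumulative dose could not tell that it stood for 56 mg/kg. Because the distortion also varies with the day of death, exposure in early deaths could not be compared fairly with exposure in survivors.

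**Working it through.** The plan gives no numerical value for this variable, so there is no stated figure to reproduce. The check applies the rule to simple dose profiles. These are assumptions chosen for arithmetic only and say nothing about treatment.

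**Inputs.** End-of-week doses d7, d14, d21 and d28 (section 3.3, with weekly collection from section 4.2); days alive t, equal to 28 for a day-28 survivor (section 3.3); unit mg/kg/day (sample data record). The 1.25 conversion scales every term alike and does not affect the ratios. I assume that a week contributes a record only if the patient is alive at its end.

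**Reading A: the recorded values are daily doses.** The rule is F = (d7 + d14 + d21 + d28) / t. For a day-28 survivor, F = 4 × (mean of the four records) / 28, which is 1/7 of that mean for any profile.

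| Profile, alive at day 28 | F | True mean (mg/kg/day) | True cumulative (mg/kg) |
|---|---|---|---|
| constant 2 | 8/28 = 0.286 | 2.0 | 56 |
| weekly steps 2, 1.5, 1, 0.5 | 5/28 = 0.179 | 1.25 | 35 |
| linear fall from 2 to 0.5 | 4.33/28 = 0.155 | 1.25 | 35 |

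Against the true 28-day mean the ratio is 0.143 for the first two profiles. For the linear fall it is 0.155/1.25 = 0.124, because an end-of-week dose is the lowest of its week. Against the true cumulative dose at a constant 2, the ratio is 0.286/56, or 1/196.

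**Deaths before day 28, reading A, constant dose.** With k completed weeks and t days alive, the ratio of F to the true mean is k/t:

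| Day of death | k | Ratio k/t |
|---|---|---|
| 27 | 3 | 0.111 |
| 21 | 3 | 0.143 |
| 20 | 2 | 0.100 |
| 14 | 2 | 0.143 |
| 13 | 1 | 0.077 |
| 6 | 0 | 0 |

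Under constant dosing the one-seventh ratio returns only when death falls at the end of a week.

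**Reading B: each term is a weekly total.** At a constant 2 the terms are 14 each and F = 56/28 = 2.0. This is the correct mean daily dose, but it is still not the cumulative dose of 56 mg/kg.

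**The case against.** The strongest reply is that the factor of seven depends on a reading the protocol does not fix. Section 3.3 gives the unit as mg/kg and not mg/kg/day. Dividing by days alive makes best sense if the terms are weekly totals, and then the arithmetic is right and only the name is wrong. The data record is offered as a sample. The weekly dose item is listed apart from the GVHD evaluations that the record serves, and a weekly total could be derived from a daily-dose field. All of this stands, and it makes the one-seventh result conditional. It does not make the two readings equally likely: the only dose field shown is in mg/kg/day, section 3.3 itself uses dose for a daily rate when it defines non-response, and no step forming weekly totals is described.

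It is also fair to say that among day-28 survivors the scale error is common to all, so their ranking by mean recorded dose is unchanged and the values can be rescaled. That does not help patients who die part-way through a week.

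A reader might infer that the trial's reported steroid exposure is wrong by a factor of seven throughout. The documents do not support this. The factor rests on reading A, applies exactly only to the mean of the four records in day-28 survivors, and becomes 196 if the comparator is the cumulative dose under constant dosing. Nor do the documents show that the variable was ever reported: it is absent from the list of correlatives in section 3.3, from Appendix C and from the SAP.

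**Conclusion.** The definition is wrong as written. On any reading it yields a per-day quantity under the name of a cumulative dose, and nothing elsewhere in the protocol or SAP corrects it.

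The size depends on the reading. On the better-supported one, daily doses in mg/kg/day, a day-28 survivor's value is one seventh of the mean of the four recorded doses. Under constant dosing the ratio for the mid-week deaths shown runs from 0 to 0.111. On the weekly-total reading there is no scale error, only a wrong name.

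The consequence is small. This is a descriptive variable, the separately recorded day-28 and day-56 doses are unaffected, and it would go too far to infer any doubt about the trial's prognostic results. The point concerns how a variable is derived and not what dose any patient should receive.

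**What to change.** Rewrite the definition in section 3.3, or in the derived-variable specification, as follows:

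1. State that the recorded values are daily doses in mg/kg/day of prednisone equivalent.
2. Multiply each value by the days alive in its week: 7, or fewer in the week of death. In the week of death use the last recorded dose, including the day-0 dose if there is no later one. Table 3 already schedules steroid dose at GVHD onset.
3. Sum these products and report the sum, undivided, as the cumulative dose in mg/kg.
4. If an average is wanted, divide the sum by days alive and call it the mean daily dose.
5. Note that end-of-week doses only approximate exposure during a taper.

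Under a constant 2 mg/kg/day this gives 56 mg/kg and a mean of 2.0 at day 28. Death on day 13 gives 7 × 2 + 6 × 2 = 26 mg/kg and a mean of 26/13 = 2.0. Death on day 6, using the day-0 dose, gives 6 × 2 = 12 mg/kg and a mean of 2.0. The linear profile shows the remaining approximation: 7 × 4.33 = 30.3 mg/kg against a true 35, about 13% low.

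If the sponsor confirms that weekly totals were collected, their undivided sum is the cumulative dose and the present quotient need only be renamed.

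The cost is a few lines of definition and a recalculation if the variable has already been derived. The weekly and onset doses that the protocol requires are enough, so no new data are needed.
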